## 10.2.2 Analysis of Secondary Outcome Measures

Secondary outcomes of dichotomised mRS (0-3 v 4-6; 0-2 v 3-6) at discharge, six and 12 months, mortality rate at 30 days, six and 12 months, re-bleeding rate and treatment-related complication rate between the arms will be compared using a chi-squared test; odds ratios will be reported. MRS at discharge and six months will be compared using a proportional odds model. These will further explain differences between the two treatment policies. Survival, time to discharge and length of ITU/HDU stay will be compared between arms using survival plots, and the log rank test will be reported. The latter two highlight differences between the two treatment arms in the NHS costs of the two treatments.

## 10.2.3 MRI sub-study Outcome Measures

Analysis of MRI data will be exploratory. Further details will be included in the Statistical Analysis Plan.

## **10.2.4** Subgroup Analyses

Odds ratios and 95% confidence intervals will be reported for the following subgroups: WFNS grade at randomisation (4/5), age band (18-50/51-65/66-80), whether there is clinically significant hydrocephalus requiring CSF drainage (yes/no), location of the site (UK/non-UK) and treatment actually received (coil vs clip). Interaction tests will be undertaken and relevant p-values will be reported.

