### 2.1 Risk Assessment

For many neurosurgeons / interventional neuroradiologists in UK neuroscience units (NSU) there is genuine uncertainty (clinical equipoise) regarding whether to treat all grade 4-5 aSAH patients as soon as possible or not; this also has service provision implications. The main risk in TOPSAT2 is that more patients would undergo aneurysm treatment, mostly by coiling, with some attendant risks that would otherwise not be the case. Some of these patients would die after coiling but before neurological improvement. We estimate this would occur, related to early treatment procedure in no more than 10-15/170 patients enrolled into the early treatment arm.

The risk of modern aneurysm coiling related-morbidity/mortality is around 3-5%, although it may be slightly higher in grade 4-5 patients (unclear from existing RCT data). However, we know that re-bleeding from an aneurysm has an awful prognosis (82% poor outcome in ISAT across all grades) and that the re-bleed rate is also higher in grade 4-5 patients.

By contrast, due to current clinical uncertainty, the potential benefits of determining the optimum management strategy for aSAH are considerable. If early treatment is proved, service reconfiguration would be necessary but the outcome for grade 4-5 aSAH patients in UK could be transformed. Studies on early treatment for grade 4-5 patients indicate good outcome rates around 50%, yet NCEPOD found many grade 4-5 patients are not admitted to a NSU in the UK. Even when patients are admitted, very few Neuroscience units provide treatment seven days per week. Furthermore, delays to treatment were correlated with poor outcome. There are almost 1300 grade 4-5 aSAH patients per annum in the UK, and NCEPOD data show that <25% currently have a good outcome, yet almost 50% might with early aggressive treatment - with substantial associated societal health benefit. Although an early intervention strategy for all grade 4-5 patients would be very expensive initially, it would carry substantial long term care and social benefits savings. However, that expense provides a strong case for the care of high grade aSAH to be truly individualised, which imaging biomarkers can potentially help to deliver.

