### 7.4 Randomisation

Randomisation will be carried out by the research team at sites through the use of a web-based system accessed via the trial website (www.topsat2.co.uk), and hosted by the Health Services Research Unit, University of Aberdeen. This service is available 24/7. Further information is

available in the randomisation SOP. The randomisation will utilise a minimisation algorithm with 80% chance of being allocated to the minimisation group to reduce differences in two arms with respect to the following (with 20% following a totally random allocation):

- Grade 4 and 5 (so distributed equally in the two arms)
- Participant age at the time of randomisation (age bands 18-50, 51-65 and 66-80)
- Presence of clinically significant hydrocephalus requiring CSF drainage procedure (yes/no)
- UK/non-UK centre.

The randomisation service will automatically confirm randomisation details to the person carrying out the randomisation, and NCTU, by email.

If the patient is randomised to the early treatment arm, the result of randomisation will be communicated to the neurovascular team who will treat the aneurysm. They will decide on the most appropriate treatment strategy but, as per the RCT evidence base, if the aneurysm is technically amenable to coiling, coiling will be the initial therapeutic option. The usual institutional surgical consent form for the procedure will then be completed and the aneurysm must be treated within 24 hours of randomisation, and 72 hours of ictal bleed that led to hospital admission.

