If the patient is randomised to the treatment after neurological improvement arm, the result will be communicated to the ITU and neurovascular team who will carry on managing the patient as per established protocol. Once the patient's neurological status improves to WFNS grade 3 or better (or GCS 13-15 or equivalent if WFNS is not assessed), the aneurysm will be treated expeditiously (by coiling, if technically amenable to coiling). According to the natural history of the disease, this improvement may take several weeks and in some may never happen. On the contrary, in some cases this may happen soon after randomisation if the patient's improvement is rapid. There will be no specific time-delay criterion for aneurysm treatment in this arm. However, it is anticipated that aneurysm treatment beyond one month post-randomisation would be exceptional; both due to the lower risk of re-bleeding after that time and the very guarded prognosis if a patient has not recovered sufficiently neurologically for treatment within one month.

A record will be kept of the actual treatment received and the date on which received, in both arms. With the patients' consent their GPs will be informed by letter about their participation in the trial.

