## **10.2 Statistical Analyses**

#### 10.2.1 Analysis of the Primary Outcome Measure

Outcome analysis will take place once all data has been collected, cleaned and the database locked. Trial analysis will be on a modified intention-to-treat basis. Where patients are lost to follow-up they will be removed from the primary outcome analysis; however a sensitivity analysis will be performed to assess the effect of missing data. The primary outcome will be a comparison of the mRS, treated as an ordinal scale, at 12 months (including death coded as 6) under the two treatment strategy arms using a proportional odds model. A sensitivity analysis will be undertaken of the proportional odds model (of primary outcome), adjusting for the minimisation criteria (WFNS grade, age band, hydrocephalus requiring drainage, and whether the patient is randomised within the UK or not). Per protocol analysis will also be performed. If a subject withdraws, all data collected up until that point will be used in trial analysis, unless he/she specifically refuses. In that case, if the trial is still recruiting an additional subject will be randomised.

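### The coil-versus-clip subgroup is defined by treatment received after randomisation, so its within-stratum odds ratios are biased against early treatment

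*Protocol*

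**What the plan says.** Section 10.2.4 states: "Odds ratios and 95% confidence intervals will be reported for the following subgroups". It then lists WFNS grade, age band, hydrocephalus needing drainage, UK or non-UK site and, fifth, "treatment actually received (coil vs clip". It adds: "Interaction tests will be undertaken and relevant p-values will be reported". The first four are the minimisation factors of section 7.4 and are known at randomisation. The fifth is not, and no caveat is attached to it.

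Section 7.4 gives the two routes to treatment:

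- **Early arm:** "the aneurysm must be treated within 24 hours of randomisation, and 72 hours of ictal bleed". No improvement is required.
- **Delayed arm:** treatment follows once the patient's "neurological status improves to WFNS grade 3 or better". The section adds that "this improvement may take several weeks and in some may never happen".

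Section 2.1 says of the additional patients who would undergo treatment under an early policy: "Some of these patients would die after coiling but before neurological improvement".

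**The concern.** A between-arm comparison within a subgroup keeps the protection of randomisation only if membership does not depend on the arm. Here it does. An early-arm patient enters the coil or clip category soon after randomisation, whatever the prognosis. A delayed-arm patient enters only by surviving and improving. A patient with the same poor prognosis therefore counts in the early side of a stratum and is absent from the delayed side.

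Coiling is the expected treatment for most patients (section 8.2), so the coil stratum will hold most of those treated. An odds ratio for coiled patients will look close to the trial's main question. It could understate a real benefit of early treatment, or suggest harm where there is none.

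**Working it through.** The protocol states no figure for this subgroup, so there is none to reproduce. The check asks which way the estimate moves and by how much under stated assumptions.

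**Inputs from the protocol**

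- Expected mRS distribution, 0 to 6 (section 10.3): 17, 10, 6, 19, 11, 10 and 27%, the last being death.
- Death is coded 6 and the model is proportional odds (section 10.2.1).
- Design odds ratio 1.7 (section 10.3).

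**Assumptions, not in the protocol**

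- The share of delayed-arm deaths, and in one scenario of mRS 5 patients, that never reach aneurysm treatment.
- In the main runs, every early-arm patient is treated.
- Treated patients are taken as one stratum, as an approximation to the coil stratum.

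**Method**

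1. The delayed arm has the section 10.3 distribution p(k). The early arm has the same distribution under no effect. For a true odds ratio of 1.7, each cumulative odds of a better score is multiplied by 1.7, which gives 25.8, 12.8, 7.0, 19.2, 9.5, 7.8 and 17.9%.
2. Let u(k) be the untreated share at score k. The treated delayed-arm distribution is p(k)[1 − u(k)] / Σ p(j)[1 − u(j)].
3. Fit one common odds ratio by proportional odds to the treated patients of both arms. Values above 1 favour early treatment.

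**One case by hand:** no true effect, half of delayed-arm deaths untreated.

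- Treated share of the delayed arm: 1 − 0.5 × 0.27 = 0.865.
- Deaths among treated delayed-arm patients: 0.135 / 0.865 = 15.6%, against 27% in the early arm.
- Odds ratio for being alive: (0.73 / 0.27) / (0.844 / 0.156) = 2.70 / 5.41 = 0.50.
- Odds ratio for mRS 0–2: the treated delayed-arm proportion is 0.33 / 0.865 = 0.3815, so (0.33 / 0.67) / (0.3815 / 0.6185) = 0.493 / 0.617 = 0.80.
- Common odds ratio over all cut points: 0.70. The true value is 1.00.

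**Results, all early-arm patients treated**

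| Untreated in the delayed arm | Delayed arm treated | OR among treated, true OR 1.0 | OR among treated, true OR 1.7 |
|---|---|---|---|
| 25% of deaths | 1 − 0.0675 = 93% | 0.85 | 1.46 |
| 33% of deaths | 1 − 0.09 = 91% | 0.80 | 1.39 |
| 50% of deaths | 1 − 0.135 = 86.5% | 0.70 | 1.23 |
| Two-thirds of deaths and half of mRS 5 | 1 − 0.18 − 0.05 = 77% | 0.55 | 0.98 |

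**Sensitivity.** Some early-arm patients may also die untreated. In the 50% scenario with no true effect, if 10% or 20% of early-arm deaths are untreated, the odds ratio is 0.75 or 0.80 instead of 0.70. In this set-up the bias disappears only if the same share of deaths goes untreated in both arms, which the two treatment rules in section 7.4 make implausible.

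**The case against.** **Both arms share one modality rule.** Under section 7.4 the aneurysm is coiled if technically amenable, in either arm. Modality among treated patients is then largely anatomical and could be seen as a near-baseline factor. That answers the choice between coil and clip. It does not answer the choice between treated and untreated, where the selection arises.

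**All randomised patients are accounted for.** The statistical analysis paragraphs of section 10.3 keep every randomised patient in the final analysis. This protects the comparison by arm, but an untreated patient still has no coil or clip category. The same paragraphs anticipate about 2% crossover from delayed to early treatment, which is too small to change the direction.

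**The size is not established.** This stands. The untreated shares are assumptions, and untreated early-arm deaths would reduce the bias.

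**Stronger readings that a reader might infer, but which the protocol does not support:**

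- *That the interaction p-value is wrong in a known direction.* The test compares the coil odds ratio with the clip odds ratio. Similar selection in both would largely cancel on the log-odds scale, while selection that differs by modality would not. The Background says grade 4–5 patients are usually not considered for clipping without substantial improvement, so a difference is possible, but its direction is not determined. The clip stratum is also expected to be small.
- *That each stratum sets the whole early arm against selected delayed-arm patients.* Each stratum holds only the early-arm patients who received that modality.
- *That the per-protocol analysis has a mirror-image bias.* Section 10.2.1 says only "Per protocol analysis will also be performed". It does not define the set by receipt of treatment, and that definition can properly be left to the SAP.

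**Conclusion.** The point holds as a defect in one planned subgroup. The direction follows from the protocol's own treatment rules: the coil and clip odds ratios, most clearly the coil one, are biased against early treatment.

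The size rests on untreated shares that the protocol does not give. Over the scenarios examined with the early arm fully treated, a null effect appears as about 0.85 down to 0.55, and a true 1.7 as about 1.46 down to 0.98. Allowing for some untreated early-arm deaths shrinks the bias without reversing it in the case examined.

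A reader might infer that the trial's main conclusion is compromised. It is not: the primary analysis compares the randomised arms on a modified intention-to-treat basis and does not use this subgroup. Severity is moderate, because the analysis affected is a secondary subgroup analysis.

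**What to change.** Take treatment received out of the section 10.2.4 list that carries between-arm odds ratios and interaction tests. Then do one of the following:

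- **Descriptive reporting.** Tabulate outcomes by modality received within each arm, showing untreated patients as their own category, with no between-arm odds ratio or interaction test. This costs only a wording change and needs no new data.
- **A baseline definition.** Define the subgroup by the modality the team intends to use, recorded before randomisation for all patients in both arms. Every patient with the item recorded then stays in a stratum, and the expected odds ratio under no effect is 1.00 in each. The cost is one extra baseline item, which will be missing for patients already enrolled. The item has to be collected: eligibility excludes some atypical aneurysms but does not record whether an aneurysm can be coiled, and section 7.4 has the neurovascular team choose the treatment after randomisation.

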# **10.2.5** Interim Analyses and Criteria for the Premature Termination of the Trial There are no planned interim primary outcome analyses.

Interim analyses will be conducted at intervals predetermined by the DMC but will include two specific time points. As there is a stop/go remit at 30 months, to ensure that the trial recruits to target, the DMC will meet at approximately 28 months to review the data for all patients recruited to 24 months. It will not be possible for them to review primary outcome as there will be few patients who will have reached the one-year primary outcome point. Patients with this condition and severity have a high mortality rate and hospital discharge is often delayed due to poor outcome. The DMC will therefore review 30-day mortality and discharge rates. The DMC will also be asked to review 30-day mortality and discharge rates after 36 months of recruitment. The results of interim analyses will be strictly confidential and the trial will only be stopped early if one or other treatment policy shows an advantage at a very high significance level.

## **10.3** Statistical Size Calculations

The outcome measure in TOPSAT2 is based on the mRS. This is a seven-point scale with values 0 to 5 representing increasing disability and a value of 6 representing death. In the past it was common to dichotomise such a scale for outcome analysis, resulting in a loss of information as not all patients contribute to the detection of a treatment effect. The Optimising Analysis of Stroke Trials (OAST) Collaboration and other authors have recently shown the benefit of ordinal analysis in the field of stroke . Using an ordinal analysis achieves substantially greater statistical power to detect a treatment effect with equal sample size. The sample size calculation is therefore based on a proportional odds regression ordinal analysis of the mRS.

The best available literature, a non-randomised study, was used to provide the expected distribution of mRS after grades 4 and 5 aSAH. Detecting a difference in clinical outcome (i.e. favouring one treatment strategy over the other) by an odds ratio of >1.5 would be compelling evidence to rapidly change to a uniform practice, as would a number needed to treat (NNT) of <10. Expected mRS distribution data (0, no symptoms 17%; 1, minor symptoms 10%; 2, some restriction in lifestyle 6%; 3, significant restriction in lifestyle 19%; 4, partially dependent 11%; 5, fully dependent 10%; 6, dead 27%) was entered into the "Sample size for ordered categories" routine of the Compare2 program in WinPepi version 11.43 July 2014 and using two-sided significance of 5%, power of 80%, and 1:1 ratio of sample size, the sample sizes needed for different odds ratios (where the odds ratio is assumed to be the same at all cutting points) were examined.

With 167 participants in each arm, a proportional odds model ordinal analysis of mRS, gives a cumulative Odds Ratio (OR) in favour of better mRS in one treatment arm of 1.7 at 5% significance level and 80% power. A margin is built in to allow for losses to follow-up and crossovers meaning a total sample size of 346 will be recruited (173 per arm). Loss to follow-up of <2% is based on data from multiple UK-based aneurysm coiling trials.

Using the expected distribution from the best available evidence as the control event rate and calculating the expected number of patients to fall in each outcome for the treatment group given an OR of 1.7 the NNT can be calculated as the inverse of the (proportion of pairwise comparisons with a better result in the treatment group – the proportion with a worse result). This gives an NNT of 5.7 (95% Cl 5.61 - 5.88).

A sample size of 346 is sufficient that some secondary outcome analyses, including a dichotomised Rankin may also reach statistical significance. For instance, for mRS 0-2 (alive and independent) vs 3-6 (dead or dependent), a 15% absolute difference in treatment effect would be detectable.

If equal numbers of grades 4 and 5 patients are recruited, with 346 patients overall, the trial is powered to detect a statistically significant odds ratio of 2.2 for improved clinical outcome, favouring one treatment strategy over the other by individual grade, particularly for grade 5. This is clinically relevant given the appreciable differences between grades 4 and 5; the optimum management strategy may differ between grades.

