#### Statistical Analysis

The Statistical Analysis Plan will be published prior to the completion of recruitment and data analysis. All randomised patients will remain in the trial whether they receive the allocated treatment or not, and will be accounted for in the final analysis. The trial is powered to account for a certain level of cross-over and drop-out from follow-up, based on ISAT/HELPS trials experience, predominantly in UK aSAH subjects. It is anticipated that there will be very few crossovers from early treatment allocation but there may be some from "treatment on neurological recovery" to "early treatment" arm – we have estimated 2% based on the TOPSAT pilot and other UK led trials involving coiling. Loss to primary outcome follow-up in ISAT at one year was 1%. In the HELPS trial for UK SAH subjects it was <2% at 18 months. We anticipate a similar or lower level of loss in TOPSAT2, particularly as the principal outcome at grades 4 and 5 will be mortality. Fairly complete death ascertainment from combined primary and secondary care electronic records is anticipated, but letter/telephone contact with a GP followed by death certification will be pursued, should any uncertain cases be identified.

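### The 346 total is what the protocol's inputs require before any allowance, so it holds no margin for losses and crossovers; power under the stated assumptions is about 77-78%, not 80%

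*Protocol*

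**What the plan says.** Protocol section 10.3 bases the sample size on a proportional odds analysis of the seven-category mRS. The expected distribution is given in full: "0, no symptoms 17%; 1, minor symptoms 10%; 2, some restriction in lifestyle 6%; 3, significant restriction in lifestyle 19"% for the better grades and, for the remaining three, "4, partially dependent 11%; 5, fully dependent 10%; 6, dead 27"%. It was entered into a named software routine for ordered categories, "using two-sided significance of 5%, power of 80%, and 1:1 ratio of sample size", with the same odds ratio assumed at every cut. The result reads "With 167 participants in each arm, a proportional odds model ordinal analysis of mRS, gives a cumulative Odds Ratio (OR"). The effect size attached to that number is worded as "in favour of better mRS in one treatment arm of 1.7 at 5% significance level and 80% power".

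The section continues: "A margin is built in to allow for losses to follow-up and crossovers meaning a total sample size of 346 will be recruited", that is 173 per arm, with loss to follow-up put below 2%. The number-needed-to-treat paragraph makes clear that the listed distribution is the control arm: "Using the expected distribution from the best available evidence as the control event rate".

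The Statistical Analysis text at the end of section 10.3 says that the trial is powered to account for some crossover and drop-out. For crossover from treatment on recovery to early treatment it says "we have estimated 2% based on the TOPSAT pilot and other UK led trials involving coiling". It also says that all randomised patients stay in the trial whatever treatment they receive. Section 10.2.1 removes patients lost to follow-up from the primary analysis and makes the primary proportional odds model unadjusted.

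**The concern.** The step from 334 (2 x 167) to 346 is presented as the allowance for losses and crossovers. It can be one only if 334 is the requirement without them. Section 10.3 gives every input, so this can be checked directly, and the check returns 346 as the starting figure.

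The stated power is then a property of the design only under perfect follow-up and adherence, while the protocol tells the reader that imperfect follow-up and adherence are already covered. That matters when a result close to the null is read against the planned power.

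**Working it through.** **Inputs (all from section 10.3 unless noted).** Control mRS 0 to 6: 0.17, 0.10, 0.06, 0.19, 0.11, 0.10, 0.27 (sum 1.00). Common OR 1.7. Two-sided 5% (z = 1.960), 80% power (z = 0.842), 1:1. Loss below 2%, taken as 2%. Crossover 2%, from treatment on recovery to early treatment.

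**Formula (Whitehead, proportional odds).** n per arm = 6 (1.960 + 0.842)^2 / [(ln OR)^2 x (1 - S)], where S is the sum of the cubed category probabilities averaged over the two arms. The factor (1 - S) is the ties term.

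**Trying to reproduce 167.** (1.960 + 0.842)^2 = 7.849 and (ln 1.7)^2 = 0.2816. Without the ties term, 6 x 7.849 / 0.2816 = 167.25 per arm. Of the variants tried, only this one gives 167, and it makes no use of the mRS distribution that the protocol says was entered.

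**Using the distribution.** Multiplying each cumulative odds of a better score by 1.7 gives treated-arm probabilities 0.258, 0.128, 0.070, 0.192, 0.095, 0.078, 0.179. The two-arm averages are 0.214, 0.114, 0.065, 0.191, 0.103, 0.089, 0.224, so S = 0.0316 and 1 - S = 0.9684. Then n = 167.25 / 0.9684 = 172.7, which rounds up to 173 per arm, or **346 in total**.

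| Variant | n per arm |
|---|---|
| Averaged probabilities, effect better than control | 172.7 |
| Averaged probabilities, effect worse than control (1 - S = 0.9531) | 175.5 |
| Control probabilities only | 173.3 |
| Treated probabilities only (better direction) | 173.1 |
| Noether, tie-corrected (better direction) | 175.7 |
| Noether, no tie correction (better direction) | 181.4 |
| Ties term dropped | 167.25 |

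The worse direction is relevant because section 10.3 speaks of an effect in favour of one arm without saying which. It needs 176 per arm, or 352 in total.

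**Power.** Power = Phi( sqrt[n (1 - S) / 6] x ln OR - 1.960 ).

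- n = 167: sqrt(26.95) x 0.5306 = 2.755, giving 78.7%.
- n = 173: sqrt(27.92) x 0.5306 = 2.804, giving 80.1%.
- n = 173 x 0.98 = 169.5 (2% lost and removed): 2.776, giving 79.3%.
- 2% loss and 2% crossover: crossovers are analysed as randomised. If they take on the early-arm outcome distribution, the delayed arm is 0.98 control + 0.02 early. The fitted common OR falls to 1.682 (ln = 0.5198), and sqrt(27.36) x 0.5198 = 2.719, giving 77.6%.

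| Scenario at OR 1.7 | Better direction | Worse direction |
|---|---|---|
| 167 per arm, no loss or crossover | 78.7% | 78.0% |
| 173 per arm, no loss or crossover | 80.1% | 79.4% |
| 173 per arm, 2% loss | 79.3% | 78.6% |
| 173 per arm, 1% loss and 2% crossover | 78.0% | 77.4% |
| 173 per arm, 2% loss and 2% crossover | 77.6% | 77.0% |

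Simulated Wilcoxon tests (200,000 replicates) agree: 78.3% at 167 per arm, 79.7% at 173, and 77.3% at 169 per arm with 2% crossover.

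**The case against.** The best defence is that the discrepancy is small. The odds ratio detectable with 80% power at 167 per arm is 1.715, which rounds to the printed 1.7. Power at 346 is 79.3% after 2% loss alone, and 2% is the upper bound of the stated loss rate. These points stand, and they are why this is a correction of wording and not a challenge to the design.

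A second defence is that, starting from 334, simple headcount inflation lands close to 346: 334 / (0.99 x 0.98) = 344 with 1% loss and 2% crossover, and 334 / (0.98 x 0.98) = 348 with 2% of each. So the margin step is roughly right by that method. This does not rescue the claim, because the fault is in the base of 334. Headcount inflation also treats crossovers as deletions, whereas the protocol keeps them in, where they dilute the effect.

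Replacement of withdrawals (section 7.8) does not help either. It applies while recruitment is open and neither replaces patients lost to follow-up nor offsets crossover.

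A reader might go further and infer that the 2% crossover rate is baseless, because the pilot had only three patients in the delayed arm. The documents do not support this: the estimate also cites other UK-led coiling trials, whose data are not shown. Nor can it be said as fact that the ties term was left out. The match to 167.25 is suggestive, but the software routine cannot be inspected.

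**Conclusion.** The point holds in a limited form. The stated inputs require about 173 per arm (about 176 in the worse direction), not 167. The 346 presented as including a margin is the requirement without one. Under the protocol's own assumptions of up to 2% loss and 2% crossover, power at OR 1.7 is about 77-78%, a shortfall of 2 to 3 points. The crossover part assumes that a delayed-arm patient treated early takes on the full early-arm outcome distribution; the protocol does not say how its 2% acts.

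A reader might infer that the trial is seriously underpowered or must be enlarged. The figures do not support that. A full 80% under 2% loss and 2% crossover would take about 368 patients (374 in the worse direction), but a gap of this size can be dealt with by stating it. A reader might equally suppose that covariate adjustment recovers the loss. Section 10.2.1 rules that out as a reason, since the primary model is unadjusted and the adjusted model is only a sensitivity analysis. Severity: should-fix.

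**What to change.** In section 10.3, replace the 167 figure and the margin sentence with text such as:

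> 173 per arm (346) gives 80% power for OR 1.7 with complete follow-up and no crossover; with 2% loss and 2% crossover, power is about 77-78%.

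Amend the sentence in the Statistical Analysis text that says the trial is powered to account for crossover and drop-out so that it gives the same figures. State the direction of effect assumed, and that crossovers are assumed to take on the early-arm outcome distribution.

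If higher crossover rates are shown (with 2% loss, about 75% power at 5% crossover and about 70% at 10%), label them as sensitivity scenarios; they are not protocol assumptions.

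The cost is a few reworded sentences and a slightly less favourable stated power. Enrolment, analysis and conduct do not change.
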